### B) Secondary outcomes

- To evaluate the total number of days for COS
- 
- To evaluate the amount of gonadotrophin consumption (IU)

## 2.4 Statistical analysis plan and sample size

The sample size was calculated assuming a non-inferiority margin of 5 eggs SD 6.7 (based on: Devroey et al. Hum Reprod. 2009;24(12):3063-72). A unilateral alpha level of 0.05 was established. With the aim to show that the difference in the mean number of collected eggs will not exceed 5, a statistical power of 80% required 30 patients per group (1:1 allocation, total sample: 60). Statistical analysis was performed using t-student test for continuous variables and chi-square test for categorical parameters. A P value of <.05 was considered significant.

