### 2. Methods

#### 2.1 Design

This is a prospective, open, randomized, self-comparative, pilot study. The type of protocol (antagonist/GnRH-a trigger) and gonadotrophin type/dose will be identical between the study and control groups; except for the day of starting the OS process in relation to the last menses. The control cycle includes a conventional previous cycle underwent by the same population in the six previous months of the randomization, thereby, decreasing inter-subject variability. The eggs from the study group will be

inseminated using IVF conventional / ICSI using partner's sperm. Fertilization will be evaluated 18-24 hours later.

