### STUDY GROUP:

Visit:	Schedule	Investigation:
Start of treatment (S1)	Beginning of gonadotrophins administration (according to randomization): 
 
- 5o day of the cycle
 
- 7o day of the cycle
 
- 9o day of the cycle
 
- 11o day of the cycle
 
- 13o day of the cycle
 
	
 
• Starting dose: identical to the dose used in the control cycle.
 
• S1 refers to the first day of ovarian stimulation
 

Visit 2 (1st control)	On the 5 o -6 o of ovarian stimulation (S5-S6)	
 
• Transvaginal scan and folliculometry
 
• Starting of GnRH antagonist (Cetrotide® )
 
• Blood samples: Estradiol, Progesterone, FSH, LH
 

Follow-up	Every 24-72 hours	
 
• Transvaginal scan and folliculometry
 

Visit 3 (Agonist)	On the day of triggering (final follicular maturation)	
 
• Transvaginal scan and folliculometry
 
• Administration of 2 ampules of Decapeptyl® (0,2 mg triptorelin acetate) with follicles 18-20 mm.
 

Visit 4 (Egg collection)	Egg collection	
 
• Transvaginal egg retrieval 36 hours after triggering.
 
• Blood samples: Estradiol, Progesterone, FSH, LH.
 

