### CONTROL GROUP:

A previous cycle underwent by the egg-donor within 6 months previously to the inclusion in the study group for the ROSE trial; in brief:

- Day 1-2 of the cycle. Transvaginal scan and follicular count. Starting of gonadotrophins 150-225 IU (Fostipur®) according to BMI and AFC (D1 of ovarian stimulation).
- Day 5-6 of ovarian stimulation. Transvaginal scan and folliculometry. Starting of GnRH antagonists (Cetrotide®) beginning with a dominant follicle  $\geq 14$  mm.
- Follow-up every 24-72 hours.
- Administration of 2 ampules of Decapeptyl® (0,2 mg triptorelin acetate) with follicles 18-20 mm to induce the final follicular maturation.
- Transvaginal egg retrieval 36 hours after triggering

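### With a true difference of 0, the stated inputs need 23 per independent group, not 30, and the total of 60 is worded for a parallel trial although donors are their own controls

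*Combined protocol and SAP*

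**What the plan says.** Section 2.4 is the only justification of the trial's size. It starts from this: "The sample size was calculated assuming a non-inferiority margin of 5 eggs SD 6.7". It then fixes the error rate: "A unilateral alpha level of 0.05 was established". Its conclusion is that "a statistical power of 80% required 30 patients per group (1:1 allocation, total sample: 60". The section gives no assumed true difference, drop-out allowance, within-donor correlation or SD of within-donor differences. It names a t-test without saying whether it is paired.

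The design sections describe a within-donor comparison. Section 2.1 calls the study self-comparative and says: "The control cycle includes a conventional previous cycle underwent by the same population in the six previous months of the randomization". The Control Group section of the overview defines the control as "A previous cycle underwent by the egg-donor within 6 months previously to the inclusion in the study group". In the Study Group table, randomization sets only the start day (5, 7, 9, 11 or 13): "Beginning of gonadotrophins administration (according to randomization".

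**The concern.** There are two separate problems.

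1. **The number.** Section 2.4 attributes the figure of 30 to 80% power at the listed inputs, but the usual calculation from those inputs gives a clearly smaller number. Some input was changed or left out. If it was alpha, the sample size rests on a different test criterion from the one printed in the same paragraph.

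2. **The unit.** Equal allocation to two groups totalling 60 describes a parallel trial. Here nobody is allocated to control. A literal reader could recruit 60 donors where 30 donors with two cycles each were meant. Section 2.1 presents self-comparison as a way to reduce variability between subjects, yet the calculation does not use the pairing.

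At stake is whether the number of women undergoing stimulation and retrieval can be checked against its justification.

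**Working it through.** **Inputs (section 2.4):** margin 5, SD 6.7, one-sided alpha 0.05, power 80%, 30 per group. **Assumption added here:** true difference 0, because none is stated.

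**Step 1. Reproduce the plan's figure, two independent groups.**

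n per group = 2(z₀.₉₅ + z₀.₈₀)² × SD² / margin²
= 2 × (1.645 + 0.842)² × 6.7² / 5² = 22.2, rounded up to **23** (46 in total).

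The non-central t calculation also gives 23 (power 0.801; with 22 it is 0.785). The plan's 30 is not reproduced: the gap is 7 per group, 14 in total.

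**Step 2. Power at the plan's 30 per group, one-sided 0.05.**

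Standard error = 6.7 × √(2/30) = 1.730. Then 5/1.730 − 1.645 = 1.245, so power is **89.4%** by the normal approximation. The non-central t gives **88.7%**.

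**Step 3. What would lead to about 30?**

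| Unstated change | Per group |
|---|---|
| One-sided 0.025, 80% power | 28.2, so 29 (normal); 30 by t (power 0.811; 29 gives 0.797) |
| One-sided 0.05, 90% power | 30.8, so 31 (normal); 32 by t |
| Two-sided equivalence at 0.05, 80% power | 30.8, so 31 (normal) |
| True difference 0.6 eggs against the margin | 28.7 (normal); 30 by t |
| True difference 0.7 eggs against the margin | 30.02 (normal); 31 by t |
| 20% drop-out | 23/0.8 = 28.75, so 29; or 24/0.8 = 30 |

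Several routes end at or next to 30. Each alters or adds to what section 2.4 states, and nothing in the document selects one.

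**Step 4. The design as described: paired, one-sided 0.05, 80% power.**

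If 6.7 is the per-cycle SD, the SD of the within-donor difference is 6.7 × √(2(1 − r)). Donors needed come from the one-sample non-central t. The correlations r are assumptions, as the document gives none.

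| Assumed r | SD of difference | Donors needed | Power with 30 donors |
|---|---|---|---|
| 0 | 9.48 | 24 | 88.0% |
| 0.3 | 7.93 | 17 | 95.8% |
| 0.5 | 6.70 | 13 | 99.0% |
| 0.7 | 5.19 | 9 | >99.9% |

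If 6.7 is already the SD of within-donor differences, 13 donors are needed and 30 give 99.0%. If 60 were read as 60 donors, power would be 99.2% even at r = 0 with 6.7 as the per-cycle SD.

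**Step 5. The unit.** Section 2.4 counts patients in two equally allocated groups. Sections 2.1 and Control Group place the same donors in both groups, and the Study Group table randomizes only among start days. The two descriptions cannot both be literal. Thirty donors contributing 60 cycles is the most natural reconciliation, but the text does not say so.

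**The case against.** The strongest reply is that nothing depends on this. Thirty exceeds 23, and 30 pairs exceed 80% power at any non-negative correlation, so the overall comparison is adequately sized under every reading examined. The study also calls itself a pilot. This stands, and it limits the weight of the point, but section 2.4 still makes a formal claim with a margin, an alpha and a power, and that claim should be checkable.

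A second reply is that the true difference of 0 is supplied here, not by the plan. A true difference of 0.6 eggs gives 30 by the t calculation (power 0.808; 29 gives 0.795) with every printed input unchanged. That is correct, and it means the calculation could be called under-specified. But zero is the conventional default, nothing in the section suggests 0.6, and a missing input is itself the gap.

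A third reply is that the design sections, read together, already imply 30 donors and 60 cycles, and that an independent-groups calculation is a common cautious substitute when the correlation is unknown (23, against 24 paired at r = 0). Both statements are reasonable. Neither appears in the plan, and the printed wording points the other way.

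**Conclusion.** The point holds. With a true difference of 0, the stated inputs require 23 per independent group, and the stated 30 corresponds to roughly 89% power, so the claim that 80% power required 30 is wrong as written. The alternative explanations are plausible, but none is documented. The equal-allocation total of 60 does not fit a design in which each donor's earlier cycle is the control.

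The error is on the safe side: it costs no power and does not threaten the trial's conclusion. It is a correction to a relied-on figure and its unit. The figures of 23 and 89% depend on the zero true difference; the paired figures depend on the assumed correlations and on what 6.7 measures. All concern the overall comparison of study with control cycles.

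**What to change.** In section 2.4:

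- Keep the stated one-sided 0.05 and write that 23 per group suffices for 80% power with a true difference of 0, and that 30 gives about 89% under independence. Alternatively, if the sponsor confirms that another alpha, a non-zero true difference or a drop-out allowance produced 30, state that input and its value.
- Replace the equal-allocation wording and the total of 60 with the number of donors, each contributing one control and one study cycle. The sponsor should confirm whether this is 30 donors and 60 cycles.
- Add the paired calculation. Say whether 6.7 is the per-cycle SD or the SD of within-donor differences and, if per-cycle, give the assumed correlation or a range of values.

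The cost is protocol and SAP wording only. No extra patients are needed and the stated test criterion does not change.

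### The trial is sized on a 5-egg non-inferiority margin, but the analysis names no comparison with that margin, no pairing, and does not say whether P<.05 is one-sided

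*Combined protocol and SAP*

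**What the plan says.** Section 2.4 sets a non-inferiority margin of 5 eggs with SD 6.7 and 80% power. It states the level, "A unilateral alpha level of 0.05 was established", and the aim, "With the aim to show that the difference in the mean number of collected eggs will not exceed 5". The resulting size is "required 30 patients per group (1:1 allocation, total sample: 60").

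The analysis takes two sentences of the same paragraph: "Statistical analysis was performed using t-student test for continuous variables and chi-square test for categorical parameters", then "A P value of <.05 was considered significant". The protocol has no other statistical text. Section 2.3 and the closing outcome sections only list what is measured.

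The design is within-donor. Section 2.1 calls it a "prospective, open, randomized, self-comparative, pilot study" and justifies the earlier conventional cycle as the control with "thereby, decreasing inter-subject variability". The Control Group section defines the control as "A previous cycle underwent by the egg-donor within 6 months previously to the inclusion in the study group".

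**The concern.** A non-inferiority claim needs a rule that sets the estimate and its uncertainty against the margin. Section 2.4 supplies the margin, the level and the aim, but the analysis sentences do not use the margin. They do not say which null hypothesis is tested, which confidence limit is compared with 5 eggs, or whether P<.05 refers to the one-sided level set earlier in the paragraph.

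Pairing is also missing. The stated benefit of self-control reaches the egg-count comparison only if the two cycles are compared within donor. The sample-size sentence instead reads like two independent groups, so it is unclear whether 60 means 60 donors or 30 donors with two cycles each.

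If the t-test is run in its usual form, against zero difference, a non-significant P could be taken as showing non-inferiority when a 5-egg loss is present. A significant P could be taken as failure when the margin is met. The study is open and the control-cycle results exist before the study cycle starts, so an unwritten rule leaves room to choose the analysis after results are seen.

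**Working it through.** **Inputs.** From section 2.4: margin 5 eggs, SD 6.7, one-sided alpha 0.05, power 80%, 30 per group. Assumed: 6.7 is the SD of a single cycle's count; counts are roughly normal; no dropout; true difference 0 for the sample size; within-donor correlation ρ of 0, 0.3 or 0.5. The documents give no ρ. If 6.7 is instead the SD of within-donor differences, the paired results equal those at ρ = 0.5.

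**The plan's own figure.** For two independent groups, n = 2[(z₁₋α + z₁₋β) × SD / margin]².
- One-sided 0.05: 2 × (2.486 × 6.7 / 5)² = 22.2, so 23 per group (also 23 with the noncentral t).
- One-sided 0.025: 2 × (2.802 × 6.7 / 5)² = 28.2, so 29 per group (30 with the noncentral t).

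The stated 30 is not reproduced at the stated level. It fits one-sided 0.025, which is the same as two-sided 0.05. Other routes come close (90% power gives 31; inflating 23 for 20% dropout gives 29), but the plan states neither. So the sidedness of P<.05 is a real question.

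**Standard errors, 30 donors.**
- Unpaired: 6.7 × √(2/30) = 1.730.
- Paired: 6.7 × √(2(1-ρ)/30) = 1.730, 1.447 and 1.223 at ρ = 0, 0.3 and 0.5.

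**Chance of P≥.05 against zero when the true loss is exactly 5 eggs, 30 donors.** Paired figures follow from the noncentral t. Unpaired figures for correlated cycles come from 200,000 simulated trials per setting.

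| Test against zero | ρ = 0 | ρ = 0.3 | ρ = 0.5 |
|---|---|---|---|
| Two-sided, unpaired | 19% | 15% | 11% |
| Two-sided, paired | 20% | 8% | 2% |
| One-sided, unpaired | 11% | about 7.5% | 4.5% |
| One-sided, paired | 12% | 4% | 1% |

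A paired test against the margin wrongly claims non-inferiority in 5% of such trials at every ρ.

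With 60 donors the two-sided figures are 1.8%/0.7%/0.2% unpaired and 2.0%/0.2%/0.01% paired.

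**Where P and the margin disagree.**
- 30 donors, unpaired: the two-sided test is non-significant up to an observed loss of 2.002 × 1.730 = 3.46 eggs. The margin is met only below 5 - 1.672 × 1.730 = 2.11 eggs. Between 2.11 and 3.46, P≥.05 and the margin is not met.
- 30 donors, paired, ρ = 0.5: significance starts at 2.045 × 1.223 = 2.50 eggs, and the margin is met below 5 - 1.699 × 1.223 = 2.92 eggs. Between these, P<.05 and the margin is met.
- 60 donors, paired, ρ = 0.5: the standard error is 6.7 × √(1/60) = 0.865, and the same window runs from 1.73 to 3.55 eggs. At an assumed true loss of 2.5 eggs, 70% of trials give P<.05 with the margin met (17% with 30 donors).

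**Cost of ignoring pairing.** The one-sided 95% half-width with 30 donors and ρ = 0.5 is 1.672 × 1.730 = 2.89 eggs unpaired, and 1.699 × 1.223 = 2.08 eggs paired. An unpaired margin test does not exceed its level: at a true loss of 5 eggs it passes in about 5%, 2.5% and 1% of trials at ρ = 0, 0.3 and 0.5. The loss is in precision, not validity.

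**The case against.** The strongest reply is that one paragraph already holds the margin, the direction, a one-sided alpha, the aim and the test family. A one-sided paired t-test against 5 eggs is then the natural reading, and the wording does not exclude it. This stands in part: the plan is incomplete rather than committed to a wrong method. It does not remove the point, because the choice that decides the trial's main claim is left to inference. Calling the study a pilot does not remove it either, since the plan sets a margin, a level and a power.

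Four stronger readings are tempting, and the documents do not support them.
- A reader might infer that the plan gives no sidedness at all. It states a one-sided alpha. What is missing is the link from that level to the P<.05 rule.
- A reader might infer that a zero-difference test always raises the false-claim rate. It does so with 30 donors and low correlation, or with a two-sided unpaired test. At the one-sided level an unpaired test is at 4.5% when ρ = 0.5, and with 60 donors the rate is about 2% or less. The self-control rationale also argues against a ρ near 0, though no value is given.
- A reader might call a significant P at a true 2.5-egg loss an error. It correctly detects a real loss. It misleads only if read as failed non-inferiority, and nothing in the plan says it would be.
- A reader might infer that the metaphase II proportion will be tested by chi-square on pooled eggs. Section 2.4 mentions no pooling, and a per-donor proportion could fall under the t-test. Pooling would treat eggs from one retrieval as independent and could inflate false positives, but by how much depends on clustering figures that the documents do not give.

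**Conclusion.** The concern holds as a gap in specification that should be fixed. The plan sizes the trial on a margin and then states no comparison with it, no pairing, and no link between P<.05 and the one-sided level. High confidence attaches to that omission, which is plain from the text.

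The consequences are conditional on a zero-difference test being used. With 30 donors, the chance that a true 5-egg loss yields a non-significant P runs from 1% to 20% across the sidedness, pairing and correlations examined, against a planned 5%. With 60 donors that risk is small, and the likelier difficulty is a significant P alongside a met margin. Either way the P value does not settle the question. These figures rest on SD 6.7 for a single count, approximate normality and assumed correlations.

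**What to change.** - **Collected eggs:** take the within-donor difference (study minus control) as the quantity of interest, estimated by a paired t-test or a mixed model with a donor effect. Claim non-inferiority only if the lower one-sided 95% limit lies above -5 eggs. This uses the plan's own margin and alpha. Say that the one-sided level governs this claim.
- **Mature eggs, stimulation days and gonadotrophin consumption:** use paired methods.
- **Metaphase II proportion and fertilization rate:** use a donor-level paired or clustered method, not a chi-square on pooled eggs.
- **Claims:** report confidence intervals, and make no non-inferiority claim for an outcome without a margin.
- **Sample:** state whether 60 means 60 donors or 30 donors with two cycles each.

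The cost is plan wording, slightly more analysis work and linking each donor's control-cycle results to her study cycle. No extra donors are needed for the analysis change. If the correlation were zero, pairing would widen the one-sided half-width only from 2.89 to 1.699 × 1.730 = 2.94 eggs with 30 donors.

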## 2.2 Study population

### a) Inclusion criteria:

- Egg-donors having at least one previous ovarian stimulation for egg-donation in our institution within the six months before being enrolled in the current trial.
- Regular cycles 27 +- 7 days
- Written / signed informed consent.

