## 2.3 Objectives

### a) Main outcome

- Total number of collected eggs
- Total number of metaphase II eggs
- Proportion of metaphase II eggs: total number/number of metaphase II

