### **Main outcome**

To evaluate and compare the total number and MII rate of eggs collected after beginning the ovarian stimulation in different moments of the follicular phase vs standard protocol.

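### Each donor is her own control, but the plan names neither a paired test nor the unit of analysis for the MII proportion

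*Combined protocol and SAP*

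**What the plan says.** Section 2.1 describes the trial this way: "This is a prospective, open, randomized, self-comparative, pilot study". The control is "a conventional previous cycle underwent by the same population in the six previous months of the randomization, thereby, decreasing inter-subject variability". The Control group section repeats that it is "A previous cycle underwent by the egg-donor within 6 months previously to the inclusion in the study group for the ROSE trial". Section 2.2 admits "Egg-donors having at least one previous ovarian stimulation for egg-donation in our institution within the six months before being enrolled", so a donor may have more than one eligible earlier cycle.

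Section 2.4 sets a margin of 5 eggs, an SD of 6.7 and a one-sided alpha of 0.05, and concludes that "a statistical power of 80% required 30 patients per group (1:1 allocation, total sample: 60". The whole analysis statement is "Statistical analysis was performed using t-student test for continuous variables and chi-square test for categorical parameters", followed by a P-value threshold of 0.05. It does not say whether the t-test is paired, whether 60 counts donors or cycles, or whether 6.7 is the SD of a single cycle or of within-donor differences. It gives no rule comparing a confidence bound with the margin.

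Section 2.3 lists among the main outcomes "Proportion of metaphase II eggs: total number/number of metaphase II". The Main outcome paragraph of the overview restates the aim as "To evaluate and compare the total number and MII rate of eggs collected after beginning the ovarian stimulation". The overview also adds fertilization rate as a secondary outcome. No unit (egg, cycle or donor) is given for either proportion.

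**The concern.** Using each donor as her own control removes between-donor variation only if the analysis works on within-donor differences. Section 2.1 gives that reduction as the reason for the design; section 2.4 is worded as if there were two separate groups. Two distinct consequences follow, and each depends on how the open wording is read.

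- **Egg count.** An unpaired t-test on paired data gives an interval that is too wide whenever a donor's two cycles are positively correlated.
- **MII proportion and fertilization rate.** A proportion of eggs, with a chi-square listed for categorical parameters, leaves room for a test on eggs pooled across donors. That test treats eggs from one cycle as independent and can report a difference that is not there. The cause is clustering of eggs within cycles; ignoring the pairing partly offsets it.

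The study is open and the control-cycle results exist before randomization. A choice of test, unit or control cycle left open now could be made after the results are known. The point concerns the overall comparison of study with control cycles, not contrasts among the five start days.

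**Working it through.** **Inputs from section 2.4:** margin 5, SD 6.7, one-sided alpha 0.05, power 80%, 30 per group. **Assumed, not in the documents:** SD 6.7 is a single-cycle SD, the same in both conditions; 30 donors with two cycles each; within-donor correlation r; intraclass correlation (ICC) of eggs within a cycle; mean 15 eggs; 80% MII.

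**1. The plan's own figure.** Two independent groups, no true difference: n = 2 × 6.7² × (z_alpha + z_power)² / 5².
- One-sided 0.05, 80%: 89.78 × (1.645 + 0.842)² / 25 = 22.2, so 23 per group.
- One-sided 0.025, 80%: 89.78 × (1.960 + 0.842)² / 25 = 28.2, so 29 (30 with the exact t).
- One-sided 0.05, 90%: 31.

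The stated 30 does not follow from the stated alpha and power together. The evidence for two-group sizing is therefore the wording about patients per group and 1:1 allocation, not this arithmetic.

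**2. Egg count, 30 donors.** SD of differences = 6.7 × √(2(1−r)). Paired SE = that SD / √30. Unpaired SE = 6.7 × √(2/30) = 1.73. The distance from the estimate to the one-sided 95% bound is t × SE, with 29 df (paired) or 58 df (unpaired). The largest observed loss that still passes is 5 minus that distance.

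| r | SD of difference | Paired SE | Unpaired / paired SE | Distance to bound, paired (unpaired 2.89) | Largest passing loss, paired (unpaired 2.11) |
|---|---|---|---|---|---|
| 0.3 | 7.93 | 1.45 | 1.20 | 2.46 | 2.54 |
| 0.5 | 6.70 | 1.22 | 1.41 | 2.08 | 2.92 |
| 0.7 | 5.19 | 0.95 | 1.83 | 1.61 | 3.39 |

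An observed loss of 2.5 eggs would thus fail unpaired and pass paired at r = 0.3.

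**3. Which way the lost precision works.** *If the bound is compared with the margin:* at a true loss of 5 eggs, the unpaired test wrongly declares non-inferiority in 2.6%, 1.1% and 0.2% of trials at r = 0.3, 0.5 and 0.7, instead of 5% (simulation). Power at zero loss is 92%, 95% and 98% unpaired, against 96%, 99% and over 99.9% paired. *If a non-significant two-sided P value is read as no difference:* by symmetry, the chance of missing a true 5-egg loss is one minus the power at one-sided 0.025. Unpaired (normal approximation), this is 1 − 0.856 = 14%, 1 − 0.896 = 10% and 1 − 0.948 = 5%. Paired, it is 1 − 0.916 = 8%, 1 − 0.977 = 2% and about 0.1%.

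**4. MII proportion, no true difference, nominal two-sided 5%, 30 donors.** Simulated beta-binomial eggs, with correlation r between a donor's two cycles. False-positive rate of a chi-square on pooled eggs:

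| ICC | r = 0 | r = 0.3 | r = 0.5 | r = 0.7 |
|---|---|---|---|---|
| 0.02 | 8.9% | 7.8% | 7.2% | 6.4% |
| 0.05 | 14.9% | 13.0% | 10.0% | 8.1% |
| 0.10 | 22.9% | 19.3% | 15.0% | 11.2% |

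A repeat run reached 23.8% at ICC 0.10, r = 0. Without clustering the rate is 4.9–5.2%. At r = 0.9 it is 5.3%, 6.2% and 6.8% for the three ICCs, and at r = 1 about 5%. Error is highest at r = 0, which identifies clustering as the cause. On per-cycle proportions, a paired t-test gives 4.8–5.3% and an unpaired one 1.3–5.0%.

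**5. Sample size in pairs.** Noncentral t, one-sided 0.05, 80% power, zero loss: 24, 17, 13 and 9 donors at r = 0, 0.3, 0.5 and 0.7. Thirty pairs at r = 0 give 88% power at one-sided 0.05 and 79.8% at one-sided 0.025.

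**The case against.** The name of the t-test in section 2.4 covers its paired form, and section 2.1 points that way. For egg count, the donor can be inferred as the unit, because section 2.4 speaks of a mean and of patients. Even an unpaired test, judged against the margin, keeps power above the planned 80%, so for a pilot this part may look like a clarification of wording. A per-cycle MII proportion can be read as a continuous variable under the t-test, with no inflation. The inflation depends on an ICC and an r that the documents do not give, and it nearly vanishes when a donor's MII rate is stable across cycles. All of this stands, and it limits the size of the point.

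It does not remove the point. The documents list no other obvious categorical outcome for the chi-square, so the pooled-egg reading is not idle. The reassurance about egg count also needs a bound-against-margin rule that section 2.4 does not state.

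A reader might infer that no rule at all identifies the control cycle. That goes too far. Sections 2.1 and Control group require a conventional cycle within six months, and the study-group table ties the starting dose to the control cycle, which implies that one has been identified before stimulation. What is open is which cycle serves when several qualify.

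**Conclusion.** The concern holds as a gap between an own-control design and an analysis statement without pairing and without a unit for MII. Taken at face value, section 2.4 gives egg-count intervals about 1.2 to 1.8 times too wide at r = 0.3–0.7. A pooled-egg chi-square would have about 6–24% error at ICC 0.02–0.10 and r = 0–0.7, and 5–7% at r = 0.9. The omission is certain; the sizes are illustrative.

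Stronger readings are tempting, but the documents do not support them:
- *The plan specifies an unpaired test, or a chi-square on pooled eggs.* It permits both and states neither.
- *An unpaired egg-count test produces false non-inferiority.* With r > 0 and a bound set against the margin, it errs the other way. The reverse reading, that it is always safe, also fails, because that rule is not written.
- *The trial is too small.* Thirty pairs suffice at one-sided 0.05 with SD 6.7, even at r = 0. This is not unconditional: power is 79.8% at one-sided 0.025, and 76% at one-sided 0.05 if the SD were 8 in both conditions (an assumption).

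This should be fixed before analysis: the better method costs almost nothing.

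**What to change.** 1. **Egg count:** paired t-test on within-donor differences (study minus control). Declare non-inferiority if the one-sided 95% lower confidence bound is above −5. Use paired t-tests also for MII count, stimulation days and gonadotrophin units.
2. **MII proportion:** state that no chi-square is run on pooled eggs. Use a paired t-test on each donor's two proportions, with a logistic GEE clustered on donor and a small-sample correction as sensitivity analysis. Do the same for fertilization only if both cycles have the data; section 2.1 describes insemination for study-group eggs only.
3. **Control cycle:** where several conventional cycles in the six-month window qualify, fix one per donor by a rule blind to its result, such as the most recent conventional cycle.
4. **Sample size:** say whether 60 means donors or cycles, and base the number on the SD of within-donor differences, with r as a stated assumption and alpha made explicit.

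The cost is SAP wording and a rewritten sample-size paragraph, with no new visits or data. Downsides: a donor missing one cycle leaves the paired estimate; r must be assumed; and unweighted proportions give small and large cycles equal weight (the GEE weights by eggs). Pairing does not remove bias from the control cycle always coming first. How cancelled or zero-egg cycles count is a separate choice that this change does not settle.
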